# 4.4.1 Permitted Therapy

### 4.4.1.1 Treatment for Symptoms of Multiple Sclerosis

The treating investigator should attempt to maintain therapies or treatments for symptoms related to MS (e.g., walking ability, spasticity, incontinence, pain, fatigue) reasonably constant throughout the study.

Ocrelizumab—F. Hoffmann-La Roche Ltd 64/Protocol WA39085, Version 10

## **Treatment of Relapses**

Patients who experience a relapse during the study may receive treatment with IV or oral corticosteroids, if judged to be clinically appropriate by the investigator. The following standardized treatment regimen may be used as warranted: methylprednisolone IV 30 mg/kg/day (maximum daily dose of 1000 mg) for 3–5 days. In addition, at the discretion of the investigator, corticosteroids may be stopped abruptly or tapered over a maximum of 10 days. Such patients should not discontinue the treatment period solely based on the occurrence of a relapse, unless the patient or investigator considers him or her to have met the criteria for withdrawal.

## 4.4.2 Prohibited Therapy

Therapies for MS noted in the exclusion criteria under Section 4.1.2.2 are not permitted during the treatment periods (i.e., 24–week dose exploratory period and during the OOE period), with the exception of systemic corticosteroids for the treatment of a relapse.

For patients who complete or withdraw from treatment with ocrelizumab, an alternative treatment for MS may be initiated as judged clinically appropriate by the treating investigator.

However, because sufficient data are not available to inform risks associated with switching to other products, the following recommendations are given:

- Caution is advised while patients remain B-cell depleted.
- Because of the unknown safety risk of administering DMTs for MS after discontinuation of ocrelizumab, certain treatments for MS such as lymphocyte–depleting agents or lymphocyte–trafficking blockers (e.g., alemtuzumab, natalizumab, fingolimod, dimethyl fumarate, cyclophosphamide, azathioprine, etc.) are strongly discouraged for as long as the patient remains B–cell depleted because of unknown effects on the immune system (e.g., increased risk, incidence, or severity of infection).

### 4.4.3 Vaccinations

See Sections 3.4.7.2, 5.1.1.3, and 5.1.5.

### 4.5 STUDY ASSESSMENTS

The schedule of activities to be performed during the study is provided in Appendix 1. All activities must be performed and documented for each patient.

Patients will be closely monitored for safety and tolerability throughout the study. Patients should be assessed for toxicity prior to each dose; dosing will occur only if the clinical assessment and local laboratory test values are acceptable.

# 4.5.1 Informed Consent and Informed Assent Forms and Screening Log

The most current, approved Institutional Review Board (IRB)/EC written Informed Consent Form for study participation signed by parent(s) or legal guardian(s), with patient informed assent obtained verbally and when possible, in writing, from all pediatric patients old enough to fully comprehend the assent document must be obtained prior to any study–specific screening procedures or assessments are performed.

Informed Consent and Assent Forms for enrolled patients and for patients who are not subsequently enrolled will be maintained at the study site. Each patient screened must be registered in the IWRS by the investigator or the investigator's research staff at screening. Reasons for screen failure must be captured in the IWRS.

A screening examination (medical history and physical examination including vital signs and weight and neurologic examination with EDSS assessment) should be performed within 8 weeks prior to the start of the study. An ECG and laboratory tests (e.g., routine safety, pregnancy test in women of childbearing potential, thyroid function tests, hepatitis screening tests, Igs, rapid plasma reagin, and CD4 count) will also be performed. The screening period can be extended to a total of 10 weeks should a laboratory blood test or baseline brain MRI scan need to be repeated for confirmation during the screening interval or for other relevant clinical, administrative, or operational reasons. Patients must fulfill all the entry criteria for participation in the study (see Section 4.1.1).

An Eligibility Screening Form documenting the investigator's assessment of each screened patient with regard to the protocol's inclusion and exclusion criteria is to be completed by the investigator. It should be stated in the medical record that the patient is participating in this clinical study.

# 4.5.2 Procedures for Enrollment of Eligible Subjects

Patient lists will be created using an IWRS. The screening ID will be allocated by IWRS. Sites should log in to the IWRS to enter the subject into screening and to register a screen failure. This log in to the IWRS should occur on Day 1 (baseline visit) after the patient's eligibility (i.e., review of inclusion/exclusion criteria) has been confirmed.

The investigator will be provided with an email notification of each patient's registration.

No patient may begin treatment prior to assignment of a medication number. Under no circumstances are patients who enroll in this study and who have completed treatment as specified permitted to be re-enrolled to this study.

The investigators will be notified by the Sponsor when the study is completed or closed to further patient enrollment.

# 4.5.3 Overview of Clinical Visits during the Study

At each visit and each telephone interview, the site should remind parents/legal guardians/patients to call the treating investigator immediately to report any changes in patient's health status (i.e., new or worsening neurologic symptoms, signs of infection, any unusual signs or symptoms since the patient left the clinic after the infusion) that may warrant an unscheduled visit.

Visits will take place as described in the schedule of activities (see Appendix 1). Visits should be scheduled with reference to the date of the baseline visit (Day 1, Visit 2).

Treatment with the first study drug infusion should occur within 24 hours of treatment allocation. In exceptional cases where all baseline assessments cannot be completed within 24 hours, the first study drug infusion can be administered within 48 hours of allocation provided that the investigator ensures that all inclusion and exclusion criteria are met on the day of dosing. In particular, there should be no evidence of an ongoing infection at the time of dosing (see criteria for re–treatment in Section 4.3.6).

For the first dose (i.e., Dose 1) ocrelizumab needs to be administered as two infusions of half the dose. A minimum interval of 20 weeks should be maintained between the second infusion (e.g., Day 15 of Dose 1) and the next infusion (e.g., Dose 2 of Week 24).

For doses administered as single infusions, a minimum of 22 weeks should be maintained between each infusion.

However, the frequency of the dose administration may be changed if emerging data from this study indicate that a different dosing frequency/regimen is more appropriate in this pediatric population. The decision to test a different dosing frequency/regimen will be endorsed by the IMC. The total maximum allowed dose is 1200 mg over 6 months.

If for logistical reasons a subsequent ocrelizumab infusion cannot be administered on the same study visit day, the infusion should be given within the next 24 hours provided that the patient still meets re-treatment criteria (see Section 4.3.6).

Patients who cannot receive their infusion at the scheduled visit or within 24 hours of the visit should be re-scheduled for a delayed dosing visit (Section 4.5.3.2).

Additional unscheduled visits for the assessment of potential relapses, new neurologic symptoms, or any other safety events may occur at any time.

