# 3.4.4 Rationale for 24-Week Re-Treatment Interval

A fixed-treatment schedule every 24 weeks should adequately maintain peripheral blood B-cell depletion as observed in the Phase III studies WA21092 and WA21093 in adults with RMS and should have the potential to confer a treatment benefit to children and adolescents with RRMS. A greater time interval between doses could result in a reduction or loss of efficacy. No clinical indices or biomarkers exist to reliably predict return of clinical activity in patients. Thus, a 24–week re-treatment interval is selected on the basis of the expected maintenance of peripheral blood B–cell depletion and the Sponsor's clinical experience with ocrelizumab in RMS as well as in PPMS. However, on the basis of emerging data from this study, the final treatment interval in pediatric patients will be confirmed for the subsequent Phase III study in children and adolescents.

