# 4.3.5 Delayed Dosing

If a scheduled dosing visit cannot occur within the time window or if an infusion cannot be administered as planned, a delayed dosing visit should be scheduled as soon as possible. To ensure that patients meet re-treatment criteria (Section 4.3.6), an unscheduled site visit (or unscheduled MN visit) should be scheduled within 2 weeks in advance of that delayed dosing visit.

The treating investigator must verify that all re-treatment criteria (Section 4.3.6), including safety laboratory parameters, are met before proceeding with the infusion of ocrelizumab. Any repeat laboratory tests must be performed, analyzed, and reviewed before administration of ocrelizumab.

Ocrelizumab should not be administered to patients with an active infection. Patients who develop infection following ocrelizumab administration should be promptly evaluated and treated appropriately. The subsequent infusion should be delayed until the infection has completely resolved and treatment with any anti–infective medications has been completed. Receipt of further ocrelizumab infusions is at the discretion of the investigator.

If the delayed dosing visit occurs more than 4 weeks from a scheduled dosing, the dose should be administered as two infusions of half the dose 14 days apart to mitigate the risk and severity of IRRs (see Section 4.3.2.3).

It is recommended that delayed infusions be administered in the morning, as patients should remain under observation for at least 1 hour after the completion of the infusion and up to 24 hours at the treating investigator's discretion.

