# 4.5.3.2 Delayed Dosing Visits

Delayed dosing visits may be scheduled only if the infusion cannot be administered at the timepoints defined in the schedule of activities (see Appendix 1). Thus, a patient who had all assessments of a dosing visit performed, but could not receive his/her infusion, should be rescheduled for the infusion.

If the delayed dosing visit occurs more than 4 weeks from a scheduled dosing, the dose will be administered as two infusions of half the dose 14 days apart to mitigate the risk and severity of IRRs (see Section 4.3.2.3).

To ensure that patients meet re-treatment criteria (see Section 4.3.6), an unscheduled site visit (or unscheduled MN visit) should be scheduled within 2 weeks in advance of any delayed dosing visit. The treating investigator must verify that all re-treatment criteria, including safety laboratory parameters, are met before proceeding with the infusion of ocrelizumab and that the benefit-risk of continuing ocrelizumab treatment is still favorable.

A delayed dosing visit should not be scheduled for the first infusion of the first dose (Dose 1, Day 1), as treatment with the first study drug infusion should occur within 24 hours of treatment allocation (in exceptional cases within 48 hours of treatment allocation provided that the investigator assures that all eligibility criteria are still met on the day of dosing).

In unforeseen situations, if the infusion of the first dose (Day 1) is delayed, then the visit for the second infusion should be scheduled 14 ( $\pm$ 2) days after the delayed first infusion.

At the delayed dosing visit, additional tests or assessments, such as routine safety laboratory tests, may be performed when the investigator judges that these are warranted.

Patients with active infection during the study should be promptly evaluated and treated appropriately; infusion should be delayed until the infection has completely resolved.

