#### 6.6 SAFETY ANALYSES

Safety data will be listed individually and summarized descriptively by cohort/dose level for the Dose Exploration period and the OOE. The exposure period (time at risk) for each safety endpoint is defined as time from the date of the first exposure to the study treatment to the date of study withdrawal or clinical cutoff date, whichever occurs earlier.

The safety endpoints include, but may not be limited to, the following:

- Incidence of adverse events (overall, by severity, and by relationship to study medication)
- Incidence of serious adverse events
- Incidence of treatment discontinuations due to adverse events
- Change from baseline by time in laboratory parameters and incidence of clinically significant laboratory abnormalities
- Change from baseline by time in vital signs (systolic blood pressure, diastolic blood pressure, pulse rate, respiratory rate, body temperature) and incidence of vital sign abnormalities

The incidence count for each adverse event will be defined as the number of patients reporting at least one treatment-emergent occurrence of the event. The incidence rate will be calculated as the incidence count divided by the total number of patients in each cohort as well as total. In addition, the rate per 100 patient-years (along with the 95% confidence interval using the exact method based on the Poisson distribution) will be calculated for all adverse events and serious adverse events.

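### After a delayed extension dose, the visit calendar, the minimum interval and the split-dose trigger count from different dates and cannot all be followed

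*Combined protocol and SAP*

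**What the plan says.** **Calendar.** Section 4.5.3: "Visits should be scheduled with reference to the date of the baseline visit". Appendix 1 lists the visits as fixed study days, for example Day 337 for Week 48 and Day 505 for Week 72, each ±6 days. Section 3.4.4 gives the planned spacing: "A fixed-treatment schedule every 24 weeks".

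**Minimum interval.** Section 4.5.3 counts from the previous infusion: "For doses administered as single infusions, a minimum of 22 weeks should be maintained between each infusion". After a dose given in two parts: "A minimum interval of 20 weeks should be maintained between the second infusion (e.g., Day 15 of Dose 1) and the next infusion".

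**Split-dose trigger.** Section 4.3.5 counts from the schedule: "If the delayed dosing visit occurs more than 4 weeks from a scheduled dosing, the dose should be administered as two infusions". Section 4.5.3.2 repeats this, and the delayed-dosing footnotes of Appendix 1 (Tables 1, 2a and 2b) count from the planned infusion date, a term left undefined. Section 4.5.3.2 also ties the delayed visit to the schedule: "Delayed dosing visits may be scheduled only if the infusion cannot be administered at the timepoints defined in the schedule of activities".

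**Analysis.** Section 6.6 lists "Change from baseline by time in laboratory parameters and incidence of clinically significant laboratory abnormalities", and Section 6.6.2 presents laboratory statistics per assessment time. Neither mentions time since the last infusion.

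**Re-anchoring.** Only two rules move a date after an earlier one has moved. The second half of Dose 1 follows a delayed first half (Section 4.5.3.2), and safety follow-up visits count from the patient's last visit (Section 3.1.1.4). Neither covers a delayed extension dose.

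**The concern.** Delays are part of the design. Section 4.3.6 suspends dosing for infection of any grade, low ANC, low CD4, low IgG or pregnancy, and Section 4.3.5 also covers missed visit windows. After such a delay the site meets three rules with three starting points and no order of precedence. Sites may resolve this differently.

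Two things follow. First, some patients may receive doses closer together than the stated minimum. Others may receive split doses because of the calendar rather than because of a long gap, and each split adds one premedicated infusion. Second, the non-dosing visits do not move. CD19, immunoglobulin and ANC values that share a week label then come from different times since dosing. Many delayed patients will be those with infections or low counts, so the shift is not random. In a cohort of 6 (Section 6.1), one such patient is one-sixth of a by-week summary.

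**Working it through.** **1. The undelayed schedule is consistent.** Study day = 7 × week + 1 gives 337 for Week 48 and 505 for Week 72, as in Appendix 1. At the extremes of the windows, (505 − 6) − (337 + 6) = 156 days = 22.3 weeks, which meets 22. From Day 15 (±3) to Week 24 (Day 169 ±6), (169 − 6) − (15 + 3) = 145 days = 20.7 weeks, which meets 20. The conflict arises only after a delay.

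**2. Keep the Day 1 date.** Let the Week 48 dose be D weeks late. A dose more than 4 weeks late is split, with the second half 2 weeks after the first. The gap to nominal Week 72 is 24 − D after a single infusion, or 22 − D from the second half of a split dose.

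| D (weeks) | Dose given | Gap to Week 72 | Stated minimum | Met? |
|---|---|---|---|---|
| 2 | Week 50 | 22 | 22 | yes |
| 3 | Week 51 | 21 | 22 | no |
| 4 | Week 52 | 20 | 22 | no |
| 5 | Weeks 53, 55 | 17 | 20 | no |
| 8 | Weeks 56, 58 | 14 | 20 | no |

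Using the +6-day window at Week 72, the limit is 24 + 6/7 − D = 22, so D is about 2.9 weeks. The last two rows assume that the 20-week rule covers split doses after Dose 1.

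**3. Keep the minimum instead.** At the shortest permitted spacing the next dose comes 22 weeks after the previous one, or 2 + 20 = 22 weeks after the first half of a split dose. Lateness therefore falls by 24 − 22 = 2 weeks per cycle. The next dose is split if D − 2 > 4, that is D > 6. At 24-week spacing lateness stays at D, so the next dose is split if D > 4.

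- D = 3, shortest spacing: next dose at Week 73, 1 week late, not split.
- D = 8, shortest spacing: lateness 8, 6, 4, 2, 0 (Weeks 56, 78, 100, 122, 144). The Week 56 dose is properly split. The Week 78 dose is one additional split. Week 100 is exactly 4 weeks late and is not split.
- D = 12, shortest spacing: lateness 12, 10, 8, 6, 4 (Weeks 60, 82, 104, 126, 148). Three additional splits, at Weeks 82, 104 and 126.
- D = 5, 24-week spacing: every later dose is 5 weeks late. From nominal Week 72 to Week 264 there are (264 − 72)/24 + 1 = 9 doses, all split.

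**4. Time since dose at fixed visits.** In Appendix 1 Table 2a the immunologic panel, which includes CD19, falls at Weeks 36, 46, 60, 70 and so on. Immunoglobulins fall at Weeks 46, 70, 94 and so on. Counted from the first infusion of the Week 48 dose, Week 60 is at 12 − D weeks and Week 70 at 22 − D. For D = 8, Week 60 CD19 is at 4 rather than 12 weeks, and Week 70 CD19 and immunoglobulins are at 14 rather than 22 weeks.

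**5. Dose exploration period.** The planned gap from Day 15 to Week 24 is 22 weeks. It drops below 20 only if the Day 15 infusion is more than 2 weeks late.

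**The case against.** The strongest reply is that this is an ambiguity and not a faulty instruction. Section 4.5.3 states the minimum as a requirement, and Section 4.5.3.2 supplies a delayed-visit route, so a site can simply wait. If the planned date is read as the re-planned date, no splitting carries over. The analyses are descriptive, safety data are also listed by patient, and Section 4.3.5 calls for an additional assessment visit within the 2 weeks before any delayed dose. No delay frequency is given, so the number of patients affected is unknown.

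Much of this stands. A reader might infer that the plan both orders a breach of the minimum and mislabels the same dose as late. It does not: for a given dose these are alternatives, depending on which rule the site keeps. A reader might also count the delayed dose itself among the calendar-driven splits, but that dose is properly split under Section 4.3.5. Nor do the documents support extending the concern to trough concentrations or the population PK model. Section 4.5.19.6 takes extension PK samples before each infusion up to Week 96, so they follow the actual dose, and Section 6.5 does not say what times the model uses.

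The reply does not remove the conflict. Section 4.5.3.2 defines a delayed visit against the schedule's timepoints, which favours the Day 1 reading. No text lets a site know that a planned date may be moved.

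**Conclusion.** The concern holds for the extension. For delays above 2 weeks (about 2.9 with the window), a site cannot keep the Day 1 calendar and the minimum interval together. If it keeps the minimum, splitting carries over to doses given no more than 24 weeks after the previous one, once the original delay exceeds 4 weeks at 24-week spacing or 6 weeks at the shortest spacing.

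Three assumptions matter. The 20-week rule is taken to cover split doses after Dose 1, although the text mentions Dose 1 only as an example. If it does not, no minimum is stated after a split extension dose: the interval conflict is then confined to delays of more than 2 and up to 4 weeks, and the 6-week threshold falls away. The 4-week threshold does not depend on this. The planned date is taken as the Day 1-based date. The length and frequency of delays are unknown, so the results are given by length of delay.

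A reader might infer that the primary 24-week PK and CD19 results are compromised. They are touched only by a delayed Day 15 infusion. The point should be corrected because stated dosing rules conflict and extension summaries ignore the actual dose date. It does not undermine dose selection from the first 24 weeks. No view is taken on which interval or split rule is clinically right.

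**What to change.** Reconcile Sections 4.5.3, 4.3.5 and 4.5.3.2 with the delayed-dosing footnotes in Appendix 1. After a delayed dose the text should state the reference date for later visits, for the minimum interval and for lateness, make these consistent, define the planned infusion date, and say whether the 20-week rule covers split doses after Dose 1. The choice is the sponsor's.

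In Section 6, add summaries of extension-period CD19, immunoglobulins and ANC by actual time since the last infusion, alongside those by nominal week.

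The cost is protocol wording, one variable derived from dates already collected, and extra summary tables. The downside is that their time windows will not match the visit numbers.

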### 4.5.3.1 Infusion Visits

It is recommended that the first infusion of ocrelizumab (Day 1 of Dose 1) should be scheduled in the morning to allow the patient to stay at the hospital (or infusion center)

with medical supervision and monitoring as required, as long as possible (e.g., until 6 p.m. or 8 p.m. according to the hospital rules), with a minimum of 1 hour after completion of the infusion. Patients may be hospitalized for a 24-hour observation after completion of the infusion at the discretion of the treating investigator.

Note: Any adverse event that results in hospitalization or prolonged hospitalization has to be reported as a serious adverse event (see Section 5.3.5.12). If the reason for hospitalization is not associated with an adverse event (e.g., for patient supervision purposes), no serious adverse event will be reported (Section 5.3.5.12).

Subsequent infusions should also be administered in the morning, as patients should remain under observation for at least 1 hour after the completion of the infusion and up to 24 hours at the treating investigator's discretion.

Physicians should alert patients that IRRs can occur within 24 hours of infusion. For this reason, a structured telephone interview will be conducted by site personnel 24 ( $\pm$ 4) hours after each infusion to identify and collect information on any changes in the patient's health status that warrant an unscheduled visit (i.e., any unusual signs or symptoms since the patient left the clinic after the infusion).

